 2.0 Final

 Date:
 10 March 2023

 EudraCT No:
 2022-003855-32

	T	
To evaluate the effect of oral administration of nirmatrelvir/ritonavir on hemodynamic response (only patients diagnosed with POTS)	Change from baseline over time as measured in delta maximum heart rate during active standing test	Estimand 1 (see above)
To evaluate the effect of oral administration of nirmatrelvir/ritonavir on fever MAPS (only patients diagnosed with POTS)	Change from baseline over time in POTS-specific symptoms as measured by MAPS	Estimand 1 (see above)
To evaluate the effect of oral administration of nirmatrelvir/ritonavir on reactive hyperemia index	Change from baseline endothelial function measured by the EndoPat® device on Day 45	Estimand 2: This estimand is intended to provide a population-level estimate of the mean treatment effect (nirmatrelvir/ritonavir relative to placebo/ritonavir) on a continuous endpoint at a given time point for all randomized/evaluable participants. The difference of Day 45 on endothelial function test between the nirmatrelvir/ritonavir and placebo/ritonavir arms in participants with long COVID estimated with an ANCOVA model that controls for baseline assessment
To evaluate the effect of oral administration of nirmatrelvir/ritonavir in 24-h average heart rate	Change from baseline over time in heart rate by ECG monitoring device	Estimand 1 (see above)
To evaluate the effect of oral administration of nirmatrelvir/ritonavir fever	Change from baseline over time in body temperature	Estimand 1 (see above)
To evaluate the effect of oral administration of nirmatrelvir/ritonavir on physical capacity	Change from baseline over time as measured by 6- minute walk test	Estimand 1 (see above)

 Version No:
 2.0 Final

 Date:
 10 March 2023

 EudraCT No:
 2022-003855-32

To evaluate the effect of oral administration of nirmatrelvir/ritonavir on handgrip strength	Change from baseline over time as measured by JAMAR	Estimand 1 (see above)
To evaluate the effect of oral administration of nirmatrelvir/ritonavir on physical activity	Change from baseline over time as measured by accelerometer	Estimand 1 (see above)
To evaluate the effect of oral administration of nirmatrelvir/ritonavir on post exertional malaise	Change from baseline at Day 90 in total score as measured by Post-Exertional Malaise short form	Estimand 2 (see above)
To evaluate the effect of oral administration of nirmatrelvir/ritonavir on fatigue	Change from baseline over time as measured by fatigue severity scale (FSS) and mental fatigue scale (MFS)	Estimand 1 (see above)
To evaluate the effect of oral administration of nirmatrelvir/ritonavir on cognitive dysfunction	Change from baseline over time as measured by MoCA test	Estimand 1 (see above)
To evaluate the effect of oral administration of nirmatrelvir/ritonavir on dyspnea	Change from baseline over time in respiratory symptoms measured by CAT and mMRC	Estimand 1 (see above)
To evaluate the effect of oral administration of nirmatrelvir/ritonavir on dysfunctional breathing patterns, maximum inspiratory pressure, and lung function	 Change from baseline over time in Njimegen questionnaire. Change from baseline over time in maximal inspiratory pressure (MIP) Change from baseline over time in forced vital capacity (FVC) and forced expiratory volume in one second (FEV1) 	 Estimand 1 (see above) Estimand 1 (see above) Estimand 1 (see above)
To evaluate the effect of oral administration of nirmatrelvir/ritonavir on plasma biomarkers	Change from baseline over time in the following plasma biomarkers: D-dimer, CRP, ESR, ferritin, NTproBNP, LD	Estimand 1 (see above)
To evaluate the effect of oral administration of nirmatrelvir/ritonavir on dysautonomia symptoms	Change from baseline over time as measured by Compass31	Estimand 1 (see above)

 Version No:
 2.0 Final

 Date:
 10 March 2023

 EudraCT No:
 2022-003855-32

Tertiary/Exploratory	Tertiary/Exploratory	Tertiary/Exploratory
To evaluate the effect of oral administration of nirmatrelvir/ritonavir on long- term measurement of breathing pattern	Change from baseline over time in Dynamic spirometry	Estimand 1 (see above)
To evaluate the effect of oral administration of nirmatrelvir/ritonavir on persistence of SARS-CoV-2 virus	Description at baseline and Day 16 of • Protein profiling using Olink Explore Inflammation panel • Nucleosome-profiling (using Volition) and circulating spike (using SIMOA™, Quanterix) • PBMC profiling for scTCR-sequencing (using BD Rhapsody) with assessment of Super-Ag mediated T-cell activation • Assessment of immune system signatures associated with disease states using mRNA-sequencing of stabilized whole blood (PaxGene).	N/A
To evaluate the effect of oral administration of nirmatrelvir/ritonavir on changes in immune cell function	Immune cell assessment by high-dimensional cytometry	N/A
To evaluate the effect of oral administration of nirmatrelvir/ritonavir on the relationship between genotypes and immune function at the molecular level	Circulating protein levels adjusted for DNA-variants	N/A

5. Study design and procedures

5.1. Overall study design

This is a phase II, interventional, randomized, parallel group, double-blind, placebo-controlled, single-center study of nirmatrelvir/ritonavir (300/100 mg) or placebo/ritonavir (100mg), administered orally twice daily for 15 days in non-hospitalized patients with post-COVID conditions.

 Version No:
 2.0 Final

 Date:
 10 March 2023

[figure not shown]
 EudraCT No:
 2022-003855-32

A total of 400 patients with post-COVID conditions will be enrolled in this study. Patients will be randomized in a ratio of 2:1 to receive either nirmatrelvir/ritonavir or placebo/ritonavir. For details, see Section 7, Study treatments.

The planned length of participation in the study for each patient is a maximum of 90 days, with potential for long-term clinical follow-up at 6 and 12 months through Electronic Medical Records and national registries. The study consists of a maximum of five visits.

The study design is outlined in Figure 1 and the planned schedule of assessments at each visit are detailed in Table 1.

Figure 1 Study design

5.2. Procedures

5.2.1. Schedule of assessments

Table 1 Schedule of assessments

Visit	Screening	Baseline	Start of Treatment	End of Treatment	Follow-up	Early Termination ^a	Follow-up
Study Day	Day -7 to Day -2	Day -1	Day 1	Day 16	Day 45	Prior to Day 90	Day 90
	Up to 7 days before baseline ^b	± 0 days		± 0 days	± 7 days		± 7 days
Informed consent	Х						
Demography	Х						
Medical history	Х						
Physical examination	Х	Х		Х	Х	Х	X
Vital signs	Х	Х		Х	Х	Х	X
Weight and height ^c	X						
Prior and concomitant therapy	Х	Х		Х	Х	Х	Х
Adjunctive therapeutic procedures	Х	Х		Х	Х	Х	X
Pregnancy test	Х			Х		Х	X
Rapid antigen testing ^d	Х	Χe					
Collect/update secondary contacts ^f		Х		Х	Х		
Randomization		Х					
Physical function tests ⁹	Х	Х		Х	Х		X
Active standing test ^h		Х		Х	Х		
Endothelial Function Test		Х			Х		
Dynamic spirometry		Х		Х	Х		X

Version No: 2.0 Final

Date: 10 March 2023 EudraCT No: 2022-003855-32

Visit	Screening	Baseline	Start of Treatment	End of Treatment	Follow-up	Early Termination ^a	Follow-up
MIP		Х		Х	Х		Х
ECG [†]		Х		Х	Х		Х
CAT ^j		Х		Х	Х		Х
Compass 31 ^j		Х			Х		Х
EQ-5D-5L ^j	Х	Х		Х	Х	Х	Х
FSS ^j		Х		Х	Х		Х
MAPS h, j		Х			Х		Х
MFS ^j		Х		Х	Х		Х
mMRC ^j		X		Х	Х		Х
MoCa ^j		X		Х	Х		Х
Nijmegen ^j		Х		Х	Х		Х
PEM ^j		X					Х
Participant-completed study intervention log			X	X			
Staff review of study diary				Х		Х	
IMP administration			X	X			
PK				Х			
Collection of IMP material (unused IMP, empty blisters, and cans)				Х	[X]	Х	[X]
Hematology, biochemistry, coagulation, and other analyses ^k	Х	Х		Х	Х		Х

Version No: 2.0 Final

Date: 10 March 2023 EudraCT No: 2022-003855-32

Visit	Screening	Baseline	Start of Treatment	End of Treatment	Follow-up	Early Termination ^a	Follow-up
Retained Research Sample for Plasma protein biomarkers		Х		Х	[X]		[X]
Retained Research Sample for Genetics		Х		Х	[X]		[X]
Retained research samples for other biomarkers		Х		Х	[X]		[X]
Adverse events ¹	Х			Х	Х	Х	Х
Long term follow up via EMRs ^m							Х

^a In case of Early Termination of treatment, the assessments should be completed as soon as possible after decision of treatment withdrawal. When possible, all study assessments should continue in accordance with the Schedule of Assessments until completion of the Day 90 visit.

^b Failure to include within 7 days may trigger repeat screening for otherwise eligible patient.

^c Height may be self-reported.

^d Only required if a participant does not have results of a positive SARS-CoV-2 test that was obtained within 5 days prior randomization. If the test is positive, subject can be re-screened at a later stage.

e At baseline, an NP swab will be collected by the investigational site staff to confirm SARS-CoV-2 infection by RT-PCR. This test will not be used to determine study eligibility. Subsequent NP or nasal swabs will be collected on Days 1, 16 and 45.

The investigator will capture contact information for at least 2 individuals who the site can contact if the participant is unable to be reached after multiple attempts.

⁹ Includes grip strength, 6-minute walk test, and accelerometer. At Screening only accelerometer assessment will be initiated.

^h Only patients diagnosed with POTS.

Apply Days 16 and 45 for up to 5 days registration.

PROs will be administered for the option to complete at home prior to next visit.

^k Laboratory tests at Days 45 and 90 are required only if clinically relevant abnormal laboratory values were present from a sample drawn at the previous study visit when laboratory assessments were performed.

SAE (s) are reported from the time point ICF is signed until Day 90 visit. AE's are reported from first intake of study treatment until Day 90 visit.

^m Potential for long-term clinical follow-up at 6 and 12 months through EMR and national registries

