 2.0 Final

 Date:
 10 March 2023

 EudraCT No:
 2022-003855-32

Study design:	Double-blinded randomized controlled trial		
Study population:	Patients with post-COVID according to WHO definition		
Number of subjects:	400		
Main inclusion criteria:	Patients, ≥18 years of age, diagnosed with post-acute COVID-19 syndrome, with reported EQ-5D-5L VAS<50		
Main exclusion criteria:	Acute COVID-19 infection, other non-related conditions with post- acute COVID-19 syndrome like symptoms, previous treatment with Paxlovid		
Investigational product(s), dosage,	Oral Nirmatrelvir/Ritonavir (Paxlovid®) 300/100 mg twice daily for 15 days		
administration:	Oral Placebo/Ritonavir 100 mg twice daily for 15 days. Randomization 2:1		
Study period:	April 2023 – April 2024		

2. Background and rationale

More than 3 years into the COVID-19 pandemic, there are still significant knowledge gaps within the umbrella definition of Post-Acute COVID-19 syndrome (PACS). Patients with PACS experience a wide variety of symptoms related to physical and cognitive function, including fatigue, dyspnea, "brain fog" or other cognitive symptoms, pain, depression, and gastrointestinal issues which significantly impact quality of life. While conclusive findings based on X-ray and blood sampling may be lacking, measurable deviations such as increased heart rate at rest, oxygen saturation upon physical activity, long-term low-grade temperature are often seen in the PACS patient.

At present there is no curative treatment for PACS at hand. Treatment is focused on symptom management and individualized rehabilitation.

We are proposing an interventional, randomized and placebo-controlled clinical intervention trial of Nirmatrelvir/Ritonavir compared with Placebo/Ritonavir in patients with post-COVID (as defined by WHO) from a database of n=988 post-COVID patients seen at the KI/KS post-COVID clinics since May 2020, and in which extensive clinical and biochemical examinations have been performed. The study will further include deep exploratory investigations of the immune phenotypes in post-COVID patients, including changes upon Nirmatrelvir/Ritonavir (Paxlovid®) treatment at the molecular and cellular level.

 Version No:

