Physical function tests: 6-minute walk test, maximal inspiratory pressure, hand grip strength, accelerometer (Active PAL) will be performed at baseline, and at Days 16, 45 and 90. The tests are non-invasive and constitute a minimal or no risk of injury and take approximately 30 minutes to perform. The physical tests that will be used are also used in the regular clinical follow-up of long COVID and for other conditions. Participants may experience fatigue during the test session, but the test procedure will be adapted to reduce this risk. The benefits of performing the measurements will outweigh the inconvenience for patients.

Patient reported outcomes: A battery of questionnaires, PRO's, will be distributed to the participants at each visit. As these can be exhausting to fill in, the possibility to bring them home for finalization will be offered, as well as the option to fill in prior to next visit.

Nasal swabs and venipuncture: Nasal swabs for antigen tests, performed at screening and baseline visits, and venipuncture for routine blood sampling as well as research blood samples will be performed at baseline, day 16, 45 and 90. They are standard procedures in routine health care and constitute no risk to the patient but may cause minor pain and discomfort.

In summary, the potential benefits of nirmatrelvir/ritonavir treatment are considered to outweigh the foreseeable risks.

 Version No:

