5.3. Biological sampling procedures

5.3.1. Handling, storage, and destruction of biological samples

Blood samples and urine (only for pregnancy test) for safety monitoring will be taken and analyzed according to local procedures. These samples will be destroyed after analysis.

Blood samples for exploratory biomarkers will be collected on Day 1, Day 16 and Day 45. These will be handled and analyzed according to predefined and agreed procedures. The samples will be kept in the biobank for a maximum of 10 years after study completion.

Saliva will be collected for antigen testing of active SARS CoV-2 infection. The sample will be taken and analyzed according to local procedures after which it will be discarded.

Nasopharynx/nasal swab will be collected to confirm SARS CoV-2 infection given positive antigen test. The sample will be taken and analyzed according to local procedures after which it will be discarded.

 Version No:

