6.3. Exclusion criteria

General exclusion criteria

- 1. Other non-related conditions with PACS like symptoms
- 2. Renal function eGFR eGFRCysC < 60 mL/min/1.73 m²
- 3. Not able to comply with the study protocol
- 4. Previous Paxlovid® treatment
- 5. Pregnancy or breastfeeding
- 6. Drug-drug interaction with ongoing treatment, including concomitant use of *any* medications or substances that are strong inducers of CYP3A4 within 28 days prior to first dose of nirmatrelvir/ritonavir and during study treatment
- 7. Participants who are planning or considering vaccination (including boosters) through Study Day 45
- 8. Active COVID-19 infection as verified by SARS CoV-2 positive antigen test
- 9. Self-reported medical conditions, including:
 - a) Type 1 or Type 2 diabetes mellitus
 - b) Chronic kidney disease
 - Neurodevelopmental disorders (e.g., cerebral palsy, Down's syndrome)
 or other conditions that confer medical complexity (e.g., genetic or
 metabolic syndromes and severe congenital anomalies)
 - d) Active cancer other than localized skin cancer, including those requiring treatment (including palliative treatment), as long as the treatment is not among the prohibited medications that must be administered/continued during the trial period.
 - e) Immunosuppressive disease (e.g., bone marrow or organ transplantation or primary immune deficiencies) OR prolonged use of immuneweakening medications:
 - i. Has received corticosteroids equivalent to prednisone ≥20 mg daily for at least 14 consecutive days within 30 days prior to study entry.
 - ii. Has received treatment with biologics (e.g., infliximab, ustekinumab, etc.), immunomodulators (e.g., methotrexate, 6MP, azathioprine, etc.), or cancer chemotherapy within 90 days prior to study entry';
 - iii. HIV infection with CD4+ cell count <200/mm³.
- 10. History of hospitalization for the medical treatment of acute COVID-19
- 11. Current need for hospitalization or anticipated need for hospitalization within 48 hours after randomization in the clinical opinion of the site investigator.
- 12. Prior/Concomitant Therapy:
 - a) Current or expected use of any medications or substances that are highly dependent on CYP3A4 for clearance, and for which elevated plasma concentrations may be associated with serious and/or life-threatening events during treatment and for 4 days after the last dose of nirmatrelvir/ritonavir. List of potential interactions provided by Pfizer provided in Appendix A.

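### Table 1 footnote d waives the antigen test for people with a recent positive result, the reverse of what an active-infection exclusion needs, and footnote e does not match the other testing rules

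*Protocol*

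**What the plan says.** Six places in the protocol bear on this.

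- **Section 6.3, exclusion criterion 8** bars "Active COVID-19 infection as verified by SARS CoV-2 positive antigen test".
- **Synopsis, main exclusion criteria**, lists "Acute COVID-19 infection, other non-related conditions with post- acute COVID-19 syndrome like symptoms" and names no test for acute infection.
- **Section 5.2.1, Table 1, footnote d**, on the label of the rapid antigen testing row (marked at screening and baseline), says of the test: "Only required if a participant does not have results of a positive SARS-CoV-2 test that was obtained within 5 days prior randomization". It adds: "If the test is positive, subject can be re-screened at a later stage".
- **Table 1, footnote e**, on the baseline cell of that row, says: "At baseline, an NP swab will be collected by the investigational site staff to confirm SARS-CoV-2 infection by RT-PCR". It continues: "This test will not be used to determine study eligibility". It also adds swabs on Days 1, 16 and 45.
- **Section 3** describes "Nasal swabs for antigen tests, performed at screening and baseline visits", with no waiver.
- **Section 5.3.1** uses saliva for antigen testing and then says: "Nasopharynx/nasal swab will be collected to confirm SARS CoV-2 infection given positive antigen test".

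Section 6.4 adds that eligibility is settled at the screening visit. Table 1 places screening on Day -7 to Day -2, and baseline and randomization on Day -1.

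**The concern.** Waiving a test because infection is already documented makes sense where infection is an entry requirement. In this trial it is an exclusion, so a recent positive is the situation in which verification matters most. Criterion 8 works only through an antigen result, and footnote d removes that result for anyone with any recent positive SARS-CoV-2 test, whatever its type.

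The passages on specimen, test and visit also disagree. Site staff cannot tell from them which test on which day decides active infection.

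The trial tests a SARS-CoV-2 antiviral in post-COVID patients. If some participants were acutely infected and the drug acted differently in them, the Day 16 EQ-5D-5L VAS contrast would average two effects. Acute infection could also affect the exploratory viral-persistence measures, such as circulating spike at baseline and Day 16.

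**Working it through.** The protocol gives no figure to reproduce on this point, so the check is a reading of the rules followed by an illustration.

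**Step 1. What happens to each kind of patient if the text is followed literally**

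| Patient | Antigen test under footnote d | Criterion 8 | Result |
|---|---|---|---|
| No recent positive, antigen test positive | Required | Met | Deferred; may be re-screened |
| Recent positive antigen test | Waived | Met by the earlier result | Excluded |
| Recent positive PCR, no antigen test | Waived | No antigen result to act on | Only the synopsis wording excludes |
| Antigen negative at screening, infected before baseline | Depends on what is done at baseline | Depends on what is done at baseline | See step 2 |
| Antigen negative, PCR positive at baseline | Done, negative | Not met | Can be randomized under footnote e; the synopsis does not settle it |

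The third row is the gap created by footnote d. Its re-screening sentence most naturally refers to the antigen test being performed, so it does not clearly cover someone whose test was waived.

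**Step 2. The baseline visit**

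By the day labels, screening falls 1 to 6 days before baseline (from Day -2 or Day -7 to Day -1). Section 3 would detect an antigen-positive infection arising in that interval, because it has an antigen test at baseline. Footnote e sits on the baseline antigen cell but describes an RT-PCR that does not count for eligibility. Section 6.4 has already settled eligibility at screening. If footnote e is taken to replace the baseline antigen test, such an infection does not stop randomization.

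**Step 3. Specimen and timing**

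- Antigen specimen: nasal swab in Section 3, saliva in Section 5.3.1.
- Nasal or nasopharyngeal swab for confirmation: at baseline without a condition in footnote e, only after a positive antigen test in Section 5.3.1.
- Later swabs: Days 1, 16 and 45 in footnote e, but the antigen row of Table 1 marks only screening and baseline, and Section 5.2.4 describes no sampling on Day 1.

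**Step 4. Possible size, on assumed inputs**

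Let f be the share of randomized patients who are acutely infected, taken as equal in both arms because of randomization. Let e be the difference between the treatment effect in them and in everyone else. The overall mean difference then shifts by f × e. The protocol gives neither value.

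- f = 1% (0.01 × 400 = 4 patients), e = 10 points: 0.01 × 10 = 0.1 point.
- f = 3% (0.03 × 400 = 12 patients), e = 20 points: 0.03 × 20 = 0.6 point.
- Extreme case, f = 10% (0.10 × 400 = 40 patients), e = 30 points: 0.10 × 30 = 3.0 points.

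The comparator is the 10-unit difference in Section 10.5. The sign of e is not known, so the shift could go either way.

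**The case against.** A reader might infer that the protocol admits acutely infected patients and so biases the result towards the drug. The documents do not support that, for these reasons.

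- **No footnote makes anyone eligible.** A schedule note on when a test is required does not override Section 6.4, under which no exclusion criterion may be met. The synopsis excludes acute COVID-19 whatever the test, and footnote d's second sentence points to deferral. The waiver can be read as sparing a repeat test in someone already known to be positive, and an investigator would probably not randomize such a person. This stands: entry is a possible result of loose wording, not a route the protocol provides.
- **Footnote e does not contradict criterion 8.** The criterion is defined by antigen alone, so a PCR that does not decide eligibility is consistent with it. In a trial whose rationale includes viral persistence, recording PCR without excluding on it is defensible. This stands. Footnote e's conflict is with Section 5.3.1 and, in part, with Section 3 and the synopsis.
- **A temporarily low VAS is not a bias.** Acute illness would lower baseline scores in both randomized arms alike. Only a different treatment effect in infected patients moves the contrast. This stands.
- **A larger benefit in infected patients is assumed.** Section 2.3 reports efficacy in high-risk acute infection, but also that the standard-risk acute trial stopped early for futility. Direction and size are open.
- **Section 3 and Table 1 largely agree.** Both place antigen testing at screening and baseline. This stands for the visits, but not for the waiver or for footnote e's replacement wording.

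The objection does not remove footnote d's reversed condition, or the lack of one consistent statement of what decides active infection.

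**Conclusion.** The point holds as an error in an operative testing rule. Footnote d's condition is the wrong way round for a trial that excludes active infection. Footnote e, criterion 8, the synopsis and Sections 3, 5.3.1 and 6.4 do not give one rule for test, specimen and visit. Followed literally, the text could let a recent PCR-positive patient, or one infected between screening and randomization, enter without the exclusion being checked.

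The effect on the primary contrast is probably small: 0.1 to 0.6 VAS points under shares of 1 to 3% and an effect difference of 10 to 20 points, with 3.0 points only under the extreme assumptions. All of these inputs are assumptions, and so is any direction. The finding rests on the text and not on these figures. A later SAP cannot correct it, because testing and eligibility are applied at enrolment.

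**What to change.** Reconcile footnotes d and e with criterion 8, the synopsis and Sections 3, 5.3.1 and 6.4, so that:

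- a recent positive result does not waive verification of the active-infection exclusion. Stating that such a result itself defers entry would serve as well as requiring the antigen test;
- the test, specimen and visit that decide active infection are given once and referred to elsewhere;
- the role of the baseline RT-PCR, and whether it is taken in everyone or only after a positive antigen test, is stated, together with the status of the Day 1, 16 and 45 swabs.

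If the baseline RT-PCR is kept for all patients, a sensitivity analysis of the primary endpoint without those PCR-positive at baseline is a cheap addition. It belongs in the SAP, to which Section 10.4 leaves sensitivity analyses, and its absence from the protocol is not a fault.

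The cost is an amendment to a few sentences and, if wanted, one further run of the primary model. A few patients may be re-screened later, which footnote d already permits after a positive test.

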4.2. Description of Objectives, Endpoints and Estimands

The primary, secondary and tertiary/exploratory objectives and endpoints assessed (as described in the schedule of activity) to assess the effect of oral Administration of nirmatrelvir/ritonavir in patients with post-COVID-19 symptoms are summarized in the table below.

Objectives	Endpoints	Estimand
Primary	Primary	Primary
To evaluate the effect of oral administration of nirmatrelvir/ritonavir at Day 16 on quality of life	Change from baseline on the EQ-5D-5L VAS scale at day 16	Estimand 1: This estimand is intended to provide a population-level estimate of the mean treatment effect (nirmatrelvir/ritonavir relative to placebo) on a continuous endpoint over time for all randomized/evaluable participants. The difference of Day 16 on EQ-5D-5L VAS scale between the nirmatrelvir/ritonavir and placebo arms in participants with long COVID estimated with a longitudinal analysis that controls for baseline assessment
Secondary	Secondary	Secondary
To evaluate the effect of oral administration of nirmatrelvir/ritonavir in patients with post-COVID-19 symptoms over time on quality of life	Change from baseline on the EQ-5D-5L VAS scale at day 45 and on Day 90	Estimand 1 (see above)

 Version No:

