5.2.2. Screening period (up to 7 days before Baseline visit)

All assessments during the study are performed as listed in Table 1.

The screening assessments are initiated after completion of the informed consent process, including provision of signed consent for participation.

SAEs are reported from the time point when the ICF has been signed.

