8.5. Safety assessments

8.5.1. Laboratory safety assessments

Hematology, biochemistry, coagulation, and other analyses will be analyzed at the Hospital Laboratory at Karolinska University Hospital, Solna. The timepoints are summarized in Table 1, Schedule of assessments. The hospital regularly reviews reference values for each of the biomarkers and the reference values are provided by the hospital lab upon delivering lab results. The reference values serve as guidance for the clinician and study team, who will judge whether a value outside of the reference value is clinically significant or not.

Hematology	Chemistry	Other
Hemoglobin	BUN or urea	Ferritin
Hematocrit	Creatinine or Cystatin-C to	Procalcitonin
RBC count	enable eGFR calculation	
Platelet count	using CKD-Epi or CKD-	Haptoglobin
WBC count	EpiCysC	
Total neutrophils (Abs)	Glucose	Thyroid function
Eosinophils (Abs)	Calcium	TSH
Monocytes (Abs)	Sodium	T4 (free)
Basophils (Abs)	Potassium	
Lymphocytes (Abs)	Chloride	Coagulation
	Total CO₂ (bicarbonate)	PT/aPTT
	AST, ALT	Fibrinogen
	Total bilirubin	D-dimer
	Albumin	
	Total protein	HIV test
	NT-proBNP	Pregnancy test (βhCG)¹
	LDH	
	hsCRP	
	ESR	

¹ A negative urine or serum (β-hCG) pregnancy test must be confirmed at screening for WOCBP only. Pregnancy tests will also be done whenever 1 menstrual cycle is missed during the active treatment period (or when potential pregnancy is otherwise suspected) and at Day 15 or ET visit.

The rapid antigen test will be evaluated directly at the clinic after testing.

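### Table 1 footnote k makes the Day 45 and Day 90 laboratory panel conditional, so the six-marker biomarker endpoint is secured for every patient only at Day 16

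*Protocol*

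**What the plan says.** - **Endpoint.** Section 4.2 lists as a secondary endpoint "Change from baseline over time in the following plasma biomarkers: D-dimer, CRP, ESR, ferritin, NTproBNP, LD". It is assigned to Estimand 1, the longitudinal estimand for randomized/evaluable participants.
- **Panel.** The table in Section 8.5.1 contains all six markers (CRP as hsCRP, LD as LDH). They belong to the Table 1 row "Hematology, biochemistry, coagulation, and other analyses", which has a plain X at Screening, Baseline and Days 16, 45 and 90.
- **Condition.** That row carries footnote k: "Laboratory tests at Days 45 and 90 are required only if clinically relevant abnormal laboratory values were present from a sample drawn" and then "at the previous study visit when laboratory assessments were performed". Under Section 8.5.1 the clinician and study team judge whether an out-of-range value matters; there is no fixed threshold.
- **Unconditional plan.** Section 3 says that "venipuncture for routine blood sampling as well as research blood samples will be performed at baseline, day 16, 45 and 90".
- **Pointers to Table 1.** Section 4.2 speaks of "endpoints assessed (as described in the schedule of activity"; Section 5.2.2 says "All assessments during the study are performed as listed in Table 1"; Section 8.5.1 says "The timepoints are summarized in Table 1, Schedule of assessments".

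**The concern.** A rule that is sensible for safety monitoring also controls the data for an efficacy endpoint. Under footnote k, a patient with no relevant abnormality at Day 16 need not be tested at Day 45. If that test is skipped, Day 16 is still the previous laboratory visit when Day 90 arrives, so no Day 90 test is required either. The patient then contributes one post-baseline value to an endpoint defined over time.

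The later results would come from a subset selected after randomization, by judgement on any analyte in the panel. That costs precision and makes the sampled patients unrepresentative. It could also bias the arm comparison if treatment changes the values that trigger sampling, or if the effect differs in patients with abnormal values. An analysis plan can model missing values but cannot recover blood that was not drawn.

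**Working it through.** **1. The texts side by side.** For the same tests on the same days, Section 3 gives no condition and footnote k gives one. Table 1 uses a plain X for this row and [X] for optional rows, but the footnote is attached to the row and qualifies its X. The three pointers above lead to Table 1. No passage says which of the two texts prevails.

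**2. Other sources of the data.** Retained research samples are bracketed at Days 45 and 90 in Table 1. Sections 5.3.1 and 5.3.2 allow later work on stored samples, but no passage assigns them to these six markers.

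**3. Patients with a required Day 45 value.** Let p be the share with a clinically relevant abnormality at Day 16. The protocol does not give p, so a range is assumed. The required number is 400p before dropout, or 207p among the completers planned in Section 10.5.

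**4. Precision at Day 45.** Let v1 be the variance of the Day 45 value given baseline, and v2 the variance given baseline and Day 16. Assume that sampling is unrelated to outcome and that nobody is tested beyond the requirement. The standard error relative to full sampling is then

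ratio = sqrt[ (v2/p + v1 − v2) / v1 ].

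The correlation is taken as 0.5 to 0.85, either equal between visits or decaying per visit. Two cells at p = 0.10:

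- Equal correlation 0.5: v1 = 0.75, v2 = 0.667; (6.667 + 0.083)/0.75 = 9.0; ratio 3.00.
- Decaying correlation 0.85: v1 = 0.478, v2 = 0.2775; (2.775 + 0.2005)/0.478 = 6.22; ratio 2.49.

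With the 48% dropout of Section 10.5 placed between Days 16 and 45, r = 0.52 and the ratio is sqrt[ (v2/(pr) + v1 − v2) / (v2/r + v1 − v2) ].

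| p | Required of 400 | Required of 207 | Ratio, no dropout | Ratio, 48% dropout |
|---|---|---|---|---|
| 10% | 40 | 21 | 2.49–3.00 | 2.75–3.07 |
| 30% | 120 | 62 | 1.53–1.75 | 1.64–1.79 |
| 50% | 200 | 104 | 1.26–1.37 | 1.31–1.39 |
| 70% | 280 | 145 | 1.12–1.18 | 1.15–1.18 |

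The cruder 1/sqrt(p) gives 3.16, 1.83 and 1.41 for the first three rows, the same order.

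**5. Precision at Day 90.** Let q, assumed 0.35 to 0.90, be the share of Day 45 samples that are again abnormal. With v1, v2 and v3 the variances of the Day 90 value given one, two and three earlier visits, the ratio is sqrt[ (v3/(pq) + (v2 − v3)/p + v1 − v2) / v1 ]. Without dropout it is 2.90–4.95, 1.7–2.9, 1.4–2.2 and 1.2–1.9 for the four values of p.

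**6. Bias.** A simulation applied the footnote visit by visit to 500,000 patients per setting, randomized 2:1. It used 36 analytes (the Section 8.5.1 panel without the HIV and pregnancy tests), each abnormal in 0.5, 1 or 3% of patients, with any analyte able to trigger the next test. The true effect was −0.50 SD, immediate or delayed to Day 45, uniform or confined to half the patients. The sampled share was 15–67% at Day 45 and 5–52% at Day 90. The longitudinal estimate was −0.47 to −0.50 at Day 45 and −0.46 to −0.51 at Day 90. The Day 90 ANCOVA estimate was −0.45 to −0.55 (Monte Carlo standard error at most 0.013). Both analyses are shown because Section 4.2 assigns the longitudinal estimand while Section 10.4 names ANCOVA for secondary endpoints.

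**The case against.** **The footnote removes a requirement and forbids nothing.** This stands. A reader might infer that the protocol drops the markers after Day 16; the documents do not say so. If sites follow Section 3, nothing is lost, so every figure above is a worst case.

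**Section 3 is a loose benefit-risk narrative.** It omits the Screening blood draw that Table 1 lists, and it puts the active standing test at Days 45 and 90 where Table 1 has Days 16 and 45. So its clash with the footnote is the weaker half of the point. The stronger half is the footnote against the endpoint, and if Section 3 carries no weight, that gap is simply real.

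**The endpoint names no days.** Also true: unlike EQ-5D VAS or the endothelial test, it does not promise Day 45 and Day 90 values in so many words. But the protocol has a separate Estimand 2 for single time points and did not use it here, and Section 10.4 plans comparisons at Days 16, 45 and 90.

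**Sampling driven by recorded values suits the planned missing-at-random handling.** Largely so, although clinical judgement enters. This answers most of the bias worry but does not restore precision.

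**The abnormality rate could be high.** A reader might take the remark in Section 2 that conclusive blood findings may be lacking as evidence of a low rate, and so of a large loss. The hypothesis statement before Section 3 points the other way, naming inflammatory phenotypes with raised D-dimer, CRP, ESR and ferritin. Neither settles p. The 10% row also lies below the 15–67% sampled in the simulation.

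**Conclusion.** The point holds as a gap in data collection for one secondary endpoint. As written, the six markers are secured in every patient only at Day 16, and the unconditional wording in Section 3 conflicts with the footnote that removes the later requirement.

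If only required samples are drawn, the Day 45 standard error rises by a factor between about 1.1 (70% abnormal at Day 16) and 3.1 (10% abnormal), and by more at Day 90. These figures rest on assumed abnormality rates and correlations and on no testing beyond the minimum.

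A reader might also infer that the treatment comparison would be seriously distorted. The simulation does not support that: the error was about 0.05 SD or less against an effect of 0.50 SD. The primary endpoint is untouched. The matter deserves correction because it is cheap to settle before the follow-up visits and cannot be repaired after them.

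**What to change.** Reconcile Section 3 with footnote k.

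- **Preferred:** require the six endpoint markers in every patient at Days 45 and 90, and keep footnote k for the other safety analytes.
- **Alternative:** restrict this endpoint to change at Day 16 in Section 4.2 and the synopsis. This gives up later follow-up of the markers. Made during the study, it changes a secondary variable, which Section 13 treats as a substantial change needing approval.

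The preferred change costs six routine assays at two visits that patients already attend. Blood volume needs a check against the 200 mL maximum in Section 5.3.3. Five full safety draws, one genetic sample and two to four research draws come to 5 × 34 + 4 + (20 to 40) = 194–214 mL, which straddles the maximum; whether it is exceeded depends on the bracketed research draws. With only the three unconditional safety draws the total is 3 × 34 + 4 + (20 to 40) = 126–146 mL. That leaves 54–74 mL, or 27–37 mL per visit at Days 45 and 90, slightly less after the Day 16 PK sample, whose volume is not stated. Use a reduced tube for the six markers, or recheck the stated maximum.
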